## 2 STUDY DESIGN

This will be a single center, single arm, open label, prospective study.

The study will be conducted in 2 enrollment stages. Initially, up to 10 healthy volunteers will be recruited and go through a short training for the use of the device followed by actual controlled use of several hours. In the second stage, up to 5 early stage ALS patients will be recruited and go through the same steps of training and device use.

Any feedback or safety concerns raised during the first stage of recruitment of healthy volunteers will be considered before moving forward to the second group of ALS patients.

The overall duration of participation for each subject will be up to 3 weeks.

The place: Rambam health care campus.

Each subject will go through a series of 4 meetings (2 meetings per week), and up to 3 hours per meeting. Meeting will be accompanied by company representatives and/or trained study team for support and guidance in each session..

Procedure will consist of an introduction and demonstration of the device features followed by actual use of the device by each subject (including control of gestures, use of menus, activation of pre- defined modes and writing full sentences). User feedback/questionnaire will be completed after the 2nd and 4th session.

The user's ability to perform each of the pre-defined tasks will be measured in each session. In addition, success rate and measured time for completion of pre-defined tasks, collected after the 4th session, will be compared to the success rate and times collected in previous sessions.

For detailed study procedures refer to section 4, as well as appendix A.

### **3 STUDY POPULATION**

The patient population is divided into two groups:

1. **Healthy volunteers**- up to 10 subjects.
2. **Early stage ALS patients** – up to 5 early stage ALS patients that can still communicate orally.

#### **3.1 INCLUSION CRITERIA**

1. Subjects 18 to 65 years old
2. Subject with understandable speaking communication
3. Subject fluent in Hebrew (speech and writing skills)

Additional inclusion criteria for Stage 2 of the study:

4. Subjects with early stage ALS diagnosis – whose speech capability is unaffected.

#### **3.2 EXCLUSION CRITERIA**

1. Subjects with glasses or contact lenses
2. Subjects with eye conditions such as Ptosis, Strabismus And Crossed Eyes
3. Medical history of epilepsy
4. Subjects who according to investigator's judgement, are unable to comply with the requirements of this protocol
5. Pregnant or lactating women.

### 3.3 SUBJECT IDENTIFICATION

A unique identification number will be assigned when an individual subject is qualified for study enrollment (based on inclusion/exclusion criteria). All enrolled subjects will be identified by the 2 digit identification number as well as their initials.

### 3.4 ENROLLMENT POINT

A subject will be considered enrolled once the use of the EyeControl is initiated according to the Instructions for Use.

Subjects withdrawn prior to this point of enrollment will be considered screen failure, and the reason will be documented in the study logs.

### 3.5 REMOVAL, REPLACEMENT, OR EARLY WITHDRAWAL OF SUBJECTS FROM TREATMENT OR ASSESSMENTS

Subjects are free to discontinue their participation in the study at any time and without prejudice to further treatment. The investigator must withdraw any subject from the study if that subject requests to be withdrawn.

The subject's participation in this study may be discontinued due to the following reasons:

- Request of regulatory agency, or sponsor or primary care physician or investigator
- Subject withdrew consent
- AE
- Investigator decides that withdrawal from the study is in the best interest of the subject.

### 3.6 HANDLING OF WITHDRAWALS

If a subject is withdrawn from the study either at his or her request or at the investigator's discretion, every effort should be made to determine the reason.

The reason for study exit (including screen failure) will be documented on the applicable CRF from.

### 3.7 STUDY TERMINATION

Eyefree assistive communication Ltd., reserves the right to discontinue the study for administrative reasons at any time, such as, but not limited to a decision to discontinue further clinical investigation with the device, improper conduct of the study by the investigator, inability to obtain the number of subjects required by the protocol, etc. Reimbursements for reasonable expenses will be made if such an action is necessary.

A principal investigator, EC, or regulatory authority may suspend or prematurely terminate participation in a clinical investigation at the investigation sites for which they are responsible.

If suspicion of an unacceptable risk to subjects arises during the clinical investigation, or when so instructed by the EC or regulatory authorities, the sponsor shall suspend the clinical investigation while the risk is assessed. The sponsor shall terminate the clinical investigation if an unacceptable risk is confirmed.

Subjects that were already included to the study must be followed according to the clinical procedures, and all information obtained for these subjects shall be reported to sponsor on the appropriate CRF.

#### **4 STUDY PROCEDURES**

Schedule of events for this study are shown in Appendix A. No protocol related procedures should be performed before written informed consent is signed as required by local regulations (i.e. subject, legal guardian, independent physician, etc). Study related events and activities including specific instructions, procedures, concomitant medications, dispensing of study device, and descriptions of AEs should be recorded in the appropriate source documents and CRF.

The study duration for each subject participating in the study will be identical.

The study duration for each subject will be approximately 2 weeks, as follows:

Screening period: one day (could be same day as procedure)

Surgery/Procedure day: 4 meetings (up to 3 hours each) which will take place over 2 weeks time.

##### **4.1 SCREENING VISIT (VISIT 0)**

The purpose as well as the risks and benefits of the procedures of the study will be fully explained to participating subjects. Those wishing to enroll in the study will sign a written informed consent prior to initiating any study related evaluations or procedures.

The following procedures should be done at the screening visit:

- Review inclusion and exclusion criteria
- Obtain medical history and demographic data
- Record prior and concomitant medications

##### **4.2 VISIT 1 (PROCEDURE DAY/ MEETING #1)**

###### **First meeting**

Subjects will be asked to arrive to the clinic. Meeting duration is expected to be up to 3 hours. Activities for the meeting are detailed hereafter:

1. **Intro to EyeControl** - explanation about the device, the components, the logic of the device etc.- ~30 min
2. **Demonstration of the EyeControl** - demonstration of the device - ~30 min
3. **Controlling the EyeControl's Joystick** - ~ 1 hour.

The user will be asked to use the logic of the joystick- the user will be asked to perform the eye gestures of: left, right, up, down and blink **-10 times for each gesture (total:50 gestures)**. A computer with a visual software feedback will be attached to the user in order to assess and present the user results. The eye movement will be recorded in this stage. Subject's face will not be recorded.

4. **The Logic of the pre-defined sentences - ~ 1 hour.**

The user will go through the menus with the guiding team to explore the options of the device and to get a feel of the device capabilities. In addition the user will be guided about the Siren mode and rest mode, and will be asked to independently turn on these modes.

5. Any adverse events will be recorded.

### 4.3 VISIT 2 (PROCEDURE DAY/ MEETING #2)

**Second meeting** – will be performed at the clinic on the same week as the 1st meeting occurred (2-3 days post 1st meeting). (Each meeting will take about 2.5 hours):

1. **Refreshing about controlling the EyeControl's Joystick- ~ 1 hour.**

The user will be asked to use the logic of the joystick - the user will be asked to perform the eye gestures of: left, right, up, down and blink **-10 times for each gesture (total: 50 gestures)**. A computer with a visual software feedback will be attached to the user in order to assess and present the user results. The eye movement will be recorded in this stage, without recording the subject's face. The user will also be asked to turn on the Siren and rest modes.

2. **Testing the logic of the pre-defined sentences - ~ 1 hour.**

The first 20 min of the meeting will be dedicated for a short re-training on the logic of the device and the pre- defined sentences. Once completed, the user will be asked to perform specific gestures to complete **10 pre-defined sentences**.

The participant will also be asked to complete a usability and feedback questionnaire at the end of meeting #2.

3. Any adverse events will be recorded.

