The camera connects to a small computer, "Odroid", which is connected to a speaker. The computer translates the pupil's movements and gives an audible sound environment. In addition, by broadcasting through Bluetooth, the patient can use various applications on their smart phone to communicate with others. An outstanding benefit is the fact that the calibration of the pupils is automatic process based on an algorithm without the need for outside aid.

The Product is based on an innovative technology that enables the eye to function as a joystick. The product is innovative (being **portable**), significantly cheaper than other products on the market, comfortable (automatic calibration and independence), Mobile (glasses and a tiny small computer), and allows the patient to communicate with the environment anywhere and anytime. **This is a revolution for patients and their surroundings – the possibility to return to social activity regaining independence and the ability to communicate with the environment.**

The solution developed consists of 3 levels: a call for help, choosing from pre-defined phrases (English and Hebrew) and composing sentences using a virtual board with the alphabet encoding. All these can be played over the loudspeaker while the user is able to hear with headset every letter/word/sentence before he chooses\ it, so that the user doesn't need the screen in front of him.

[figure not shown]

Chart 1: The product

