## 1.7 STUDY ENDPOINTS

### Primary endpoint:

Assessment of the feasibility of the use of EyeControl device, measured by:

- **Ability to perform device features:**
  - Controlling the EyeControl's Joystick [measured by successful correct performance of over 70% of the gestures].
  - Controlling the Rest mode and Siren mode [measured by successful correct performance of over 70% of the gestures].
  - Testing the logic of the pre-defined sentences;
    - a. ability to say 10 pre-defined sentences [over 80% success rate];
    - b. Time - perform each sentence in less than 2 minutes – [over 80% success rate for all sentences].
  - Controlling the application and Free text features –words per minute, using the application Alphabet
- **Required Training time/ learning curve of;**
  - pre-defined device features [selected results after the 4th meeting compared with results results of previous meetings]
  - free speech [selected results after the 4th meeting compared with results after the 3rd meeting]
- **Usability** feedback (user experience) questionnaire completed by each user.

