### 5.3.2 Installation & Calibration

The device arrives ready for activation. The user/caregiver should plug it in to a battery or an electrical outlet and wait until the "All set" sound is spoken through the speaker. The calibration process begins several seconds afterwards.

The user will hear "Calibration" in earphone.

Then he will hear "1", "2", "3" which are corresponding to three stages of calibration.

We recommend the following:

- After the "Calibration" – the user should blink few times to allow the camera spot the area of interest – when he will hear "1" he can stop blink.
- After "1" he can look straight at the camera – to allow the camera to spot the pupil – when he will hear "2" he can stop look at the camera.
- After "2" he user can move his eye randomly to all sides – to allow the camera to understand the range of movement of the pupil. When the user hear the word "3" he can stop do that, and the calibration is actually over.

The whole calibration stage should take 5-10 seconds.

After calibration stage the user immediately gets to the main menu which is described in the next section.

There is no visual display for the device, but it can be described schematically in the following way:

words										
levels	directions	questions	hygiene	family	in hospital	in bed	clothing	general	actions	feelings
0-9	left, right,..., forward	why, who,..., where	tissue, toilet,...	father,..., grandson	nurse,..., doctor	light,...,tv	pants,...,shirt	yes, no,..., more, less	give, take,..., sleep	happy,...,frustrated

Chart 2: Navigation schema

To navigate between the words options, a user needs to look left or right.

To make a selection of a specific word, for example “father” the user need to look few times left or right (the menu is cyclic) until he hear “family” in the earphone, then he need to look down in order to hear “Father”. If he wants to say “Father” in the speaker he needs to blink to confirm.

Next to the words menu (look left or right) there are more menus which allow the user to connect to the application or to be in rest mode or to change settings.

application	rest mode	settings		
		toggle earphone language	toggle speaker language	toggle gender

Chart 3: The menus schema

- To choose any option that you hear- A blink.

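### The joystick success rate is measured only in combined practice-and-test blocks with a visual-feedback computer attached, so it may overstate performance in intended, display-free use

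*Protocol*

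**What the plan says.** Protocol Section 1.7 lists the joystick criterion as a component of the primary endpoint: "Controlling the EyeControl's Joystick [measured by successful correct performance of over 70% of the gestures".

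Sections 4.2 (meeting 1) and 4.3 (meeting 2) each describe one joystick block of about an hour, with five gestures performed "10 times for each gesture (total: 50 gestures" in all). Both sections describe the set-up in the same sentence: "A computer with a visual software feedback will be attached to the user in order to assess and present the user results". The meeting 2 block is headed "Refreshing about controlling the EyeControl's Joystick- ~ 1 hour".

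Section 2 says who attends: "Meeting will be accompanied by company representatives and/or trained study team for support and guidance in each session".

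On how the device works in use, Section 5.3.2 says "There is no visual display for the device". Section 1.3 presents this as a product feature: the user hears each item before choosing it, "so that the user doesn't need the screen in front of him". Section 5.3.4 confirms that the user first hears the word in the headphone.

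The tests listed for meetings 3 and 4 (Sections 4.4 and 4.5) cover pre-defined sentences, opening the application and writing words. They contain no 50-gesture joystick test.

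**The concern.** The same computer scores the gestures and presents the results, and it is attached to the person being tested. The natural reading is that the user sees how each gesture was registered and can adjust to it. That visual aid is absent from the device as it will be used. The joystick blocks have no stated point at which training ends and the test begins, and nothing says that staff withhold help while the 50 gestures are counted.

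At stake is what the joystick figure means. If the plan is followed as written, every joystick observation comes from these conditions. A pass would show control of the device with an added display and possibly with help, which is a weaker finding than control in intended use. This is settled when the data are collected: if no gestures are recorded without the visual aid, no later analysis can supply them.

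**Working it through.** There is no stated figure to reproduce: Section 9 reports that no formal sample size calculation was made, and no power or error rate is given.

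**1. How much of the joystick data is affected.** Section 4 describes two tests of 50 gestures, so 2 × 50 = 100 per subject. With up to 10 + 5 = 15 subjects, that is at most 15 × 100 = 1,500 gestures, all collected with the visual-feedback computer attached. Section 2 does say that ability on each pre-defined task is measured in every session, but Section 4 describes no joystick test after meeting 2.

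**2. How the other tasks are handled.**

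| Task | Separation of training and test | Screen |
|---|---|---|
| Sentences, meeting 2 (4.3) | 20 minutes of re-training, then the 10 sentences | Feedback computer not mentioned |
| Application, meeting 3 (4.4) | Instructor-guided use is one item, the test a later item | Smartphone application |
| Alphabet, meeting 3 (4.4) | Test content specified | Explicitly done without the screen |
| Siren and rest modes, meeting 1 (4.2) | Guided first, then turned on independently | Feedback computer not mentioned |
| Joystick, meetings 1 and 2 (4.2, 4.3) | None stated within the block; called a refresher at meeting 2 | Feedback computer attached |

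The Protocol draws the needed distinction for other tasks but not for the joystick.

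**3. Where on the scale it would matter.** 35/50 = 70.0% is not over 70%; 36/50 = 72.0% is. So a pass needs at least 36 correct. Assume that the criterion is applied to one user and one 50-gesture test, and that gestures are independent with a common success probability p. Then

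P(pass) = Σ (k = 36 to 50) C(50, k) p^k (1 − p)^(50 − k).

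| p | P(pass) |
|---|---|
| 0.55 | about 1% |
| 0.60 | 5.4% |
| 0.65 | 18.8% |
| 0.70 | 44.7% |
| 0.75 | 74.8% |
| 0.80 | 93.9% |
| 0.85 | 99.5% |

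From 0.65 to 0.75 the chance of passing rises by 74.8 − 18.8 = 56.0 points. From 0.80 to 0.85 it rises by 99.5 − 93.9 = 5.6 points. The table shows how sensitive the criterion is to a shift in p. It does not say how large a shift the display or guidance would cause, and the Protocol gives nothing from which to estimate one.

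**4. Whether there is time for a separate test.** Each joystick block is given about 60 minutes for 50 gestures, or 60/50 = 1.2 minutes per gesture. The meeting 1 items already add up to 30 + 30 + 60 + 60 = 180 minutes, the full three hours, so the practice part has to fit inside the joystick hour. At 1.2 minutes per gesture there appears to be room.

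**The case against.** The strongest reply is that this is an ambiguity in one component of a small first-in-human proof of concept. Several parts of that reply stand.

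- **Timing and audience of the feedback.** The text does not say to whom results are presented, or whether this happens during or after the 50 gestures. Live display to the user is the natural reading, not an explicit statement.
- **Feedback in real use.** A reader might infer that the user cannot correct gaze or blink in real use. Sections 5.3.2 and 5.3.4 do not support that: the headphone responds as the user navigates. Only the visual channel is extra.
- **Other tasks.** A reader might extend the screen problem to sentences and words. The feedback computer is described only for the joystick blocks, and training and testing are largely separated elsewhere. Sentences, which are also produced by gestures, are tested at meetings 2, 3 and 4 without mention of that computer, so feasibility does not rest on the joystick alone.
- **Who scores.** A reader might suppose that company staff judge success. No section says so. The computer assesses, eye movement is recorded, and attendance may be by company representatives, study team or both.
- **Showing results to learners.** This is a reasonable choice during training.

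What the reply does not remove is that no joystick test without the feedback computer is described, and that neither its visibility to the user nor prompting is restricted during scoring. If the display is meant for the assessor only, the Protocol needs to say so.

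**Conclusion.** The point holds for the joystick component only. As written, its over-70% criterion is measured solely in blocks that mix practice with scoring, with a visual-feedback computer attached and staff on hand to help, while the device in use has no visual display. The result may overstate performance under intended use.

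A reader might go further and conclude that the primary success rate is biased upward. The document does not show this. The joystick is one of several primary components; the direction is plausible but not demonstrated, since watching a screen could also disturb pupil gestures; and the size is unknown. The binomial table rests on independent gestures and a per-user, single-test reading of the criterion. It supports only the statement that test conditions matter mainly for users near the 70% line and hardly at all for users well above 80%. No sample size, power or error-rate figure is affected. This is a cheap improvement to a measurement procedure.

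**What to change.** Amend the joystick items in Sections 4.2 and 4.3:

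- Split each block into a practice part, where visual feedback and guidance are allowed, and a scored part of 50 gestures.
- In the scored part, make the display visible to the assessor only. Keep the device's own audio feedback.
- Give no prompting in the scored part, and count any prompted gesture as not successful. Calling out which gesture to perform is the test instruction and is not a prompt.
- Score from the software record, which the set-up described appears to produce already.

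The cost is about one paragraph of text, with the same equipment, staff, visits and meeting length. The downside is that the joystick success rate may come out lower.

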### 4.4 VISIT 3 (PROCEDURE DAY / MEETING #3)

**Third meeting** - to be performed 1 week after the 1st meeting.

Activities for the meeting are detailed hereafter:

1. **Learning about the application:** Reviewing the manuals of the application, the different options, the logic etc. - ~30 min.
2. **Using the application (with guidance of instructor):** Writing free sentences, using the features of the application, calling for help, going to rest mode etc. - ~1 hour.
3. **Using the full logic of the EyeControl:** ~30 min

The user will be asked to go through the menus and turn on the application, and compose full sentences using the system. *(The tests in this session will focus on the*

*application features. The test will include also the pre-defined sentences and the idea is to show the learning curve when compared to the Second meeting of the pre- defined sentences). The test will include: 5 pre-defined sentences, Opening the application and writing 2-3 Words.*

**Using the Alpha Bet feature / free text:** writing the alphabet without the screen.  

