- An "I need your help!" siren – 3 blinks (each blink should be about 0.25 seconds long). All three blinks should be executed in 4 seconds (default x = 4, can be configured in configuration file). If for example the user is making:
  - Blink1, Right, Blink2, Blink3 – that will count as two blinks (blink2 and blink3) If he will make another blink 4 seconds after blink2, a siren will be played.
- Going out of Rest Mode:
  - Looking Down- Center- Down- Center- Down- Center in 4 seconds.
- Getting in to Rest Mode: via menu or by making a sequence of
  - Blink-Up-Blink-Up in 4 seconds

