### 5.3.3 Top Menu

- The **Settings** menu includes the following options
  - Toggle earphone language – select the language you will hear on earphone
    - English or Hebrew (other languages will be available in the future)
  - Toggle speaker language – select the language you and others will hear on speaker
    - English or Hebrew (other languages will be available in the future)
  - Toggle gender – select the gender of the voice heard on earphone and speaker
    - Male or Female

- **Rest mode**- A mode in which the application does not respond to the eyes' movements of the user. This mode allows the user to rest or look in different directions without activating the system, for example, in the middle of a treatment. In order to switch back from Rest Mode to regular Activation Mode, the user must look down quickly 3 times (Down- Center- Down- Center- Down) in a 4 seconds time frame. Outside of this sequence of gestures, there is another sequence that allows the user to express distress (3 quick blinks). These are the only two gestures sequences that are activated during Rest Mode. A partial execution of these commands will not be effective after 4 seconds since the beginning of the sequence.
- **Application** - Choosing the Application option results in trying to connect the device via Bluetooth, to a smartphone that went through Pairing in advance. In the case that the connection attempt is successful, the device goes from playing pre-recorded words/siren or settings menu mode to a mode in which eye gestures are sent to the app and there they're converted to letters and free speech. To return to the regular mode in which the user hears the pre-recorded words through a headphone/speaker, the companion will close the app on the smartphone.

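### Rest-mode control is a primary-endpoint item, but subjects are only asked to enter the mode; the separate timed exit is never requested or scored

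*Protocol*

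**What the plan says.** The endpoint, in section 1.7 and again in the synopsis, reads "Controlling the Rest mode and Siren mode [measured by successful correct performance of over 70% of the gestures". It does not say which gestures are meant or how many attempts are made.

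The tasks are in section 4:
- Meeting 1 (4.2): after guidance on the two modes, the user "will be asked to independently turn on these modes".
- Meeting 2 (4.3): "The user will also be asked to turn on the Siren and rest modes".
- Meeting 3 (4.4): the instructor-guided block covers "Writing free sentences, using the features of the application, calling for help, going to rest mode etc". The test itself is listed separately: "The test will include: 5 pre-defined sentences, Opening the application and writing 2-3 Words". It has no rest-mode or siren item.
- Meeting 4 (4.5): the listed test is five pre-defined sentences, opening the application, and five words in each of two writing modes. It has no rest-mode or siren item either.

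Section 2 also describes device use in terms of activating the modes.

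Section 5.3 describes more than activation. Rest mode can be entered through the menu or by a blink-and-up sequence within 4 seconds. While it is on, only the exit sequence and the distress call work. The exit sequence is given in 5.3.2 as "Looking Down- Center- Down- Center- Down- Center in 4 seconds" and in 5.3.3 as "the user must look down quickly 3 times (Down- Center- Down- Center- Down) in a 4 seconds time frame".

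**The concern.** Controlling a mode means being able to switch it on and off. Here the two directions use different actions. Entry is possible by ordinary menu navigation, which is already exercised elsewhere. Exit needs a dedicated sequence inside a 4-second window, and it is the step that gives the user back the words menu and free text. The plan asks for the first and not the second.

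What is at stake is the feasibility conclusion. If the visits are run exactly as described, there will be no planned data on exit, and the report could still claim that rest-mode control was shown. A statistical analysis plan cannot repair this later, because it cannot analyse an action that no visit asks for.

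**Working it through.** The protocol states no figure for this item beyond the over-70% threshold, and section 9 reports no formal sample size calculation, so there is nothing to reproduce. The check has four steps.

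**1. Endpoint against tasks.** The parts of section 5.3 that a user performs, set against section 4:
- Enter rest mode: asked for at meetings 1 and 2; guided practice at meeting 3.
- Sound the siren: asked for at meetings 1 and 2; guided practice (calling for help) at meeting 3.
- Leave rest mode: not asked for at any meeting.

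**2. Effect on the score.** Assumption: *k* attempts at each task, because the protocol gives no number. The proportions do not depend on *k*. Take a subject who always enters rest mode, always sounds the siren and never exits.
- Tasks as written (enter, siren): 2k/2k = 100%, over the threshold.
- Exit added as an equal third task: 2k/3k = 66.7%, not over it.
- Rest mode alone (enter, exit): k/2k = 50%, not over it.

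**3. Whether adding exit to the pool is enough.** If a further item that the subject passes is also pooled, the score is 3k/4k = 75%, over the threshold again. Even with three items, a subject who exits on a fraction *p* of attempts scores (2 + p)/3, which exceeds 0.70 once p > 0.10. With 10 attempts per task, borrowed from the joystick test for illustration, two successful exits give (10 + 10 + 2)/30 = 73.3%, a pass with 20% exit success. Exit therefore needs its own threshold.

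**4. Counting single movements instead of tasks.** The phrase *the gestures* could mean elements of a sequence. Entry by gesture has 4 elements. The siren has 3 blinks in 5.3.2 and 5.3.3, but the text headed Calling for Help, after 5.3.5, gives 4. Exit can be counted as 3 down-looks, as 5 elements (5.3.3) or as 6 (5.3.2). The same subject then scores (4 + siren)/(4 + siren + exit):
- 3-blink siren: 7/10 = 70.0%, 7/12 = 58.3%, 7/13 = 53.8%; none is over 70%.
- 4-blink siren: 8/11 = 72.7%, 8/13 = 61.5%, 8/14 = 57.1%; only the first is over 70%.

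The unreconciled descriptions can therefore move a score across the threshold. They can also change whether a single exit is correct: a third down-look inside 4 seconds followed by a late return to centre succeeds under 5.3.3 and fails under 5.3.2.

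**The case against.** The strongest objection is that the endpoint refers to the gestures without limiting them to entry, and section 5.3 lists the exit sequence among the rest-mode gestures. A reader might infer that the protocol counts a subject stuck in rest mode as a success, with 100% recorded where 0% is deserved. The documents do not support that. No such scoring rule is stated, there is no attempt count, and there is no rule for combining rest mode with siren. The 0% appears only under an all-or-nothing cycle that is not in the protocol. This part of the objection stands. It does not supply the missing task: every instruction in section 4 stops at turning on or going to the mode.

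Second, exit is probably exercised in practice. At meeting 2 the ten pre-defined sentences come after rest mode has been turned on, and they cannot be produced while it is active. Staff attend every session, so a stuck subject would be seen. That is fair, but nothing says the exit is recorded, and staff are there to give support, so an aided exit would not be told apart from an unaided one.

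Third, it is tempting to say that the device's silence in rest mode should also be scored. Not responding to eye movements is mainly a property of the device, while this endpoint concerns the user's ability. Sections 5.8 and 8 already provide for reporting malfunctions. That objection stands.

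Last, this is a first-in-human proof of concept in up to 15 subjects, all able to speak, and rest mode is half of one item among several. The point therefore concerns what the study can conclude, not harm to participants.

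**Conclusion.** The point holds in this form: a primary-endpoint item on controlling rest mode is fed only by tasks of turning it on, and no meeting asks for or scores the timed exit. As written, the conclusion on rest-mode control would rest on entry alone.

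The size depends on scoring that the protocol does not fix. With equal attempts per task, the subject who never exits goes from 100% to 66.7% or 50%, which is enough to change the result at the threshold. These figures illustrate the gap; they do not describe a stated scoring rule. The absent attempt count is part of the same defect: the joystick test has 50 gestures as its denominator, and this item has none. The change is worth making before enrolment because it is cheap and the data cannot be recovered afterwards.

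**What to change.** - In section 4.3 at least, ask the subject to enter rest mode by either permitted route and then to leave it unaided. Record entry and exit separately, with an exit that needed help counted as not achieved.
- Fix the number of attempts for entry, exit and siren, as is done for the joystick gestures, and say how exit is counted when entry fails.
- State in section 1.7 that exit is part of the item, and apply the over-70% rule to exit on its own, not pooled with entry and siren.
- Record any device output during rest mode as a device deficiency under section 8, not as a failure by the user.
- Before the first subject, reconcile the exit sequence in 5.3.2 (ends on centre) with 5.3.3 (ends on down), and the help call in 5.3.2 and 5.3.3 (3 blinks) with the text under Calling for Help (4 blinks).

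The cost is protocol wording, a CRF line and a few extra minutes within the existing session. The success rate may look less favourable than with entry-only scoring.
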